 - $b = -[1 + r + \hat{p}_T + r * \hat{p}_C - \delta * (r + 2)]$
 - $c = \delta^2 - \delta(2 * \hat{p}_T + r + 1) + \hat{p}_T + r * \hat{p}_C$
 - $d = \hat{p}_T * \delta * (1 - \delta)$
 - $w = (\pi + \cos^{-1}(v/(u^3)))/3$
 - $v = b^3 / (3a)^3 - (b * c) / (6a^2) + d / (2a)$
 - $u = \text{sign}(v)[b^2 / (3a)^2 - c / (3a)]^{1/2}$

Based on \hat{p}_T, \hat{p}_C and the Farrington-Manning variance estimate \hat{v}_0 , the realization T_0 of the test-statistic

$$T = \frac{\hat{p}_T - \hat{p}_C + \delta}{\sqrt{\hat{v}_0}}$$

will be obtained. The p-value of the Farrington-Manning test regarding non-inferiority will be determined by calculating the probability

$$p = P(X > T_0)$$

where X is a standard normally distributed random variable.

Furthermore the 80% -confidence interval of the difference in responder rates

$$CI = [\hat{p}_T - \hat{p}_C - z_{1-\alpha} * \sqrt{\hat{v}_0}, \hat{p}_T - \hat{p}_C + z_{1-\alpha} * \sqrt{\hat{v}_0}]$$

will be determined, where $z_{1-\alpha}$ is the $(1 - \alpha)$ -quantile of the standard normal distribution with $\alpha = 0.1$.

Handling missing data

The above elaboration describes the analysis procedure in the event of no missing data. For the proposed imputation method missing at random (MAR) will be assumed.

Information on the pain assessments during the last 3 days of treatment in the Treatment Period might only be partially available. In this case *Multiple Imputation* will be used to impute missing values:

1. For each treatment group, a multivariate normal distribution for the vector of the age group (AGE), underlying pain condition (PAIN) and baseline pain intensity (BASE), as well as the last 6 scheduled pain measurements during treatment of the Treatment Period, denoted by (Y_1, \dots, Y_6) , is assumed $(AGE, PAIN, BASE, Y_1, \dots, Y_6) \sim MVN(\mu, \Sigma)$. Missing observations are assumed to depend on the observed values of the subjects in the same treatment group. Therefore, in both treatment arms, missing pain assessments will be imputed using information from an imputation model that is only based on the subjects in the respective arm..

The multiple imputation will be performed once for all subjects using VAS, and once for all subjects using FPS-R. To ensure that the imputed values are within the range of the respective pain scale (0-10 for FPS-R and 0-100 for VAS), minimum and maximum values for the variable to be imputed should be specified.

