The multiple imputations will be done via SAS PROC MI. The imputation model will be based on the default Markov chain Monte Carlo (MCMC) method for general patterns of missingness (Dmitrienko et al. 2005). A BY statement will be used to implement the imputation by treatment group. The variables will be given the following order: age group, pain condition, baseline pain, last 6 scheduled pain assessments starting with the earliest one.

For the sake of reproducibility of the results, the seed for pseudo-random number generation will be set to 550366.

The number K of imputed data sets will be set to 200, resulting in 200 complete data sets:

- Number of imputed data sets: $K = 200$

Imputed values for missing baseline pain intensities, to be used as explanatory variable in the logistic regression model, will also be obtained from the multiple imputation.

2. Each complete data set $k = 1, \dots, K$ will be analyzed as described above in case of no missing data up to the step where $\hat{p}_{T,k}$, $\hat{p}_{C,k}$ and the Farrington-Manning variance estimate $\hat{v}_{0,k}$ are obtained. Let $\hat{\theta}_k = \hat{p}_{T,k} - \hat{p}_{C,k}$.

3. With $(\hat{\theta}_1, \sqrt{\hat{v}_{0,1}}), \dots, (\hat{\theta}_{200}, \sqrt{\hat{v}_{0,200}})$ as input, PROC MIANALYZE will be applied to obtain the test statistic T_{MI} and confidence interval CI_{MI} as follows:

- Multiple imputation estimate: $\hat{\theta}_{MI} = \frac{1}{K} \sum_{k=1}^K \hat{\theta}_k$
- Within-imputation component of variance: $\hat{\sigma}_w^2 = \frac{1}{K} \sum_{k=1}^K \hat{\sigma}_k^2$
- Between-imputation component of variance: $\hat{\sigma}_b^2 = \frac{1}{K-1} \sum_{k=1}^K (\hat{\theta}_k - \hat{\theta}_{MI})^2$
- Multiple imputation variance estimate: $\hat{\sigma}_{MI}^2 = \left(1 + \frac{1}{K}\right) \hat{\sigma}_b^2 + \hat{\sigma}_w^2$
- Test statistic: $T_{MI} = \frac{\hat{\theta}_{MI} + \delta}{\hat{\sigma}_{MI}}$
- Degrees of freedom: $\vartheta = (K - 1) \left[1 + \frac{\hat{\sigma}_w^2}{(1 + \frac{1}{K}) \hat{\sigma}_b^2} \right]^2$
- Confidence interval:

$$CI_{MI} = [\hat{\theta}_{MI} - \hat{\sigma}_{MI}^2 t_{\vartheta, 1-\alpha}, \hat{\theta}_{MI} + \hat{\sigma}_{MI}^2 t_{\vartheta, 1-\alpha}]$$

with $t_{\vartheta,1-\alpha}$ being the $(1 - \alpha)$ -quantile of the t -distribution with $\alpha = 0.1$ and ϑ degrees of freedom.

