Non-inferiority of tapentadol versus morphine will be assigned if the lower bound of CI_{MI} exceeds the negative non-inferiority margin $-\delta = -0.2$. Additionally, the realization $T_{MI,0}$ of the test statistics T_{MI} will be used to compute the one-sided p-value

$$p = P(X > T_{MI,0})$$

where X is a t-distributed random variable with ϑ degrees of freedom.

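### The multiple-imputation interval that decides non-inferiority is printed with the variance where the standard error belongs, so it can contradict the plan's own p-value; one Farrington-Manning line may carry a second slip

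*SAP*

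**What the plan says.** SAP 18.1.8.2 gives two routes to the primary interval. The first applies when no pain score is missing ("The above elaboration describes the analysis procedure in the event of no missing data"). Its lower limit is "p}_T - \hat{p}_C - z_{1-\alpha} * \sqrt{\hat{v}_0", a normal quantile times the square root of the Farrington-Manning variance.

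The second applies when any of the last six scheduled pain scores has to be imputed. Step 3 starts from the 200 estimates and the square roots of their variances, and says of these: "as input, PROC MIANALYZE will be applied to obtain the test statistic" and the interval. It then lists the formulas:

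- σ²_MI is labelled "Multiple imputation variance estimate" and is the within-imputation plus the inflated between-imputation variance.
- The test statistic is "T_{MI} = \frac{\hat{\theta}_{MI} + \delta}{\hat{\sigma}_{MI", so it divides by σ_MI.
- The interval is "\theta}_{MI} - \hat{\sigma}_{MI}^2 t_{\vartheta, 1-\alpha" for the lower limit, with the same squared term in the upper limit.

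The decision follows: "Non-inferiority of tapentadol versus morphine will be assigned if the lower bound of" this interval exceeds -0.2. The test statistic "will be used to compute the one-sided p-value", as an addition.

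Earlier in the same section, the restricted tapentadol rate p̃_T comes from a closed-form cubic. The restricted morphine rate is printed as the *unrestricted* tapentadol estimate p̂_T plus δ.

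**The concern.** A t-based interval is the estimate plus or minus the quantile times the standard error. Here the quantile multiplies the variance, so the interval and the test statistic two lines above it are on different scales and cannot both be right. The plan gives the interval the deciding vote and reports the p-value alongside it. Coded literally, one output could show non-inferiority by the interval and p well above 0.1, and the conclusion would follow the wrong one. Because the standard error is below 1, squaring it can only narrow the interval, so every discrepancy favours success.

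The second point is distinct. Farrington-Manning estimates both rates under the null, so they must differ by exactly δ, which requires p̃_C = p̃_T + δ. Using p̂_T + δ breaks that constraint, can give a morphine rate above 1, and can make the variance negative. It enters the interval and the p-value alike, so it cannot cause them to disagree.

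**Working it through.** **Inputs.** From SAP 5.2: margin δ = 0.2, one-sided α = 0.1, 80% responders in both arms, 69 subjects at 2:1 (46 tapentadol, 23 morphine). The normal 0.90 quantile is 1.2816. The calculations use raw proportions without the covariate model. The per-dataset variance σ²_k is not defined in the list; I take it to be v₀,k.

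**Reproducing the plan's figure.** Maximising the restricted likelihood numerically at 80%/80% gives p̃_T = 0.694, matching the SAP's cubic. Then p̃_C = 0.894 and

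v₀ = 0.694 × 0.306/46 + 0.894 × 0.106/23 ≈ 0.0087, SE ≈ 0.093.

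Enumerating all 47 × 24 outcomes, the standard-error rule has power 80.8% at 80%/80%. The planned 69 subjects and 80% power are reproduced.

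**The two rules side by side.** Non-inferiority is declared when

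- standard-error rule: θ > -0.2 + 1.2816 × SE
- printed rule: θ > -0.2 + 1.2816 × SE²

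With SE = 0.10 the thresholds are -0.072 and -0.187. For SE from 0.08 to 0.14 the printed interval covers only about 8% to 14%, not 80%.

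**One data set.** Take 28/46 = 0.6087 and 18/23 = 0.7826, so θ = -0.1739, with no added imputation variance. The restricted rates are 0.5976 and 0.7976, giving

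v₀ = 0.5976 × 0.4024/46 + 0.7976 × 0.2024/23 = 0.01225, SE = 0.1107.

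- Printed lower bound: -0.1739 - 1.2816 × 0.01225 = -0.190, non-inferior.
- Standard-error lower bound: -0.1739 - 1.2816 × 0.1107 = -0.316, not shown.
- T = (-0.1739 + 0.2)/0.1107 = 0.24, p = 0.41.

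With 18/23 on morphine, the standard-error rule first passes at 33/46: θ = -0.0652, SE = 0.1018, lower bound -0.196, p = 0.093.

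**Exact operating characteristics, σ²_MI = v₀.**

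| True rates (tapentadol/morphine) | Printed rule accepts | Standard-error rule accepts | Opposite verdicts |
|---|---|---|---|
| 60% / 80% (at the margin) | 43.7% | 10.5% | 33% |
| 80% / 80% | 96.9% | 80.8% | 16% |

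**Allowing for imputation variance.** Missing information λ is assumed at 5%, 10% and 20%. Total variance is set to v₀/(1 - λ), with K = 200 and the SAP's degrees of freedom (79600, 19900, 4975). The point estimate stays at its complete-data value, which is an approximation. At 60%/80% the printed rule stays at 43.7%, while the standard-error rule gives 10.2%, 9.0% and 8.0%. Non-inferior by the interval with p > 0.1 then occurs in 34% to 36% of trials at 60%/80% and 18% to 22% at 80%/80%. The example above at λ = 10% gives a bound of -0.191 and p = 0.41.

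**The Farrington-Manning line alone, interval corrected.** At 80%/80% the printed morphine rate is 0.80 + 0.20 = 1.00 instead of 0.894, and v₀ falls from 0.0087 to 0.0046. Error at the margin:

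| Morphine rate | As printed (undefined v₀ counted as failure) | With p̃_T + δ |
|---|---|---|
| 80% | 12.0% | 10.5% |
| 90% | 14.3% | 11.2% |

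Counting undefined variances as acceptances changes the first column only to 12.0% and 14.5%. At 80%/80% the plugged-in rate exceeds 1 in 56% of trials and v₀ is not positive in 5.7%. Power there is 79.0% or 84.7%, depending on how those trials are scored. The cubic's coefficients a, b, c and d are correct.

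**The case against.** The strongest reply is that the SAP already settles which interval is meant. Step 3 names PROC MIANALYZE and feeds it square-root variances, and the procedure would return a standard-error interval. The test statistic and the complete-data interval are both on the standard-error scale. The change log for SAP Amendment 01 (17.2) shows the inputs being moved to that scale. SAP 13.1.1 and Protocol 14.2.6.1 call for an 80% interval, which the printed formula is not. On this reading it is a notation slip in a programming appendix, and 43.7% arises only if someone bypasses the named procedure and ignores a conflicting p-value.

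Most of that stands. The intention is clear, and 43.7% is not the trial's expected error rate. But the SAP says the procedure yields the interval by the formulas that follow, and then prints a different one. Section 18.1 exists to guide SAS coding, and a contract research organization does the analysis. A validator checking output against the text would find a mismatch in the primary result.

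It is also fair that the missing-information levels are assumed and that holding the point estimate fixed drives part of the trend. The core figures do not depend on them.

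Finally, both points rest on typeset symbols. For the interval, the square stands in both limits and is absent from the test statistic just above, so a misreading is unlikely. For the Farrington-Manning line, one hat in place of a tilde is the whole evidence, and that remains a query.

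**Conclusion.** The interval error holds with high confidence as an error in the written primary decision rule. It must be corrected because it sits on the confirmatory conclusion and can only favour it. Its effect is conditional: it arises only when multiple imputation is used and the printed line is coded by hand. In that case the nominal 10% one-sided error becomes about 44% at the planned morphine rate, and interval and p-value conflict in roughly a third of trials at the margin. The sizes assume 46 and 23 subjects and unadjusted proportions.

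The Farrington-Manning line is a separate, lower-confidence point. If the accent is as printed, error at the margin rises by 1.5 points at a morphine rate of 80% (12.0% against 10.5%) and by about 3 points at 90% (14.3% against 11.2%), and the variance is sometimes undefined. It adds nothing to the 43.7%.

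**What to change.** In SAP 18.1.8.2, step 3, write the interval as θ_MI ± σ_MI × t(ϑ, 1-α), in both limits. Check the line defining the restricted morphine rate against the original SAP; if it carries a hat, change it to p̃_C = p̃_T + δ. Add a programming check that the lower bound exceeds -0.2 if and only if the one-sided p-value is below 0.1. The cost is one symbol, one accent if confirmed, and a line of validation code. No new data or further analysis is needed.

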18.1.8.3 Bayesian analysis – Details

A sensitivity analysis will be carried out by fitting a Bayesian logistic regression model to compare the proportion of responders under tapentadol PR and morphine PR. Odds ratios will be calculated. Treatment response is the dependent variable and treatment arm, age group at baseline (ageg), underlying pain condition (cancer/non-cancer-related pain), age group x baseline VAS, and age group x baseline FPS-R are possible (but not limited to) explanatory variables. The age group refers to a variable indicating whether, on the basis of the subject's age, to use the VAS pain assessment (for subjects aged 12 years to less than 18 years) in the model, or to use the FPS-R score (for subjects aged 6 years to less than 12 years). The treatment variable should be introduced in the model as an indicator variable with value 0 for subjects in Tapentadol and value 1 for subjects in Morphine.

Specifically, if X_i is the response indicator for subject i , then we will assume:

$$X_i \sim \text{Bernoulli}(\lambda_i)$$

$$\log(\lambda_i / (1 - \lambda_i)) = \beta_0 + \beta_1 \text{ageg}_i + \beta_2 \text{cancer}_i + \beta_3 (\text{ageg}_i * \text{baseline VAS}_i) + \beta_4 (1 - \text{ageg}_i) * \text{baseline FPS-R}_i + \beta_5 \text{treatment}_i + \varepsilon_i$$

Non-informative flat normal priors with zero mean and variance equal to 1000 will be assigned to the regression coefficients β_1 to β_4 . The prior for the treatment effect β_5 (on the log-odds scale) will be a normal distribution with mean = 0.10 and standard deviation = 0.48; this prior distribution has been derived from the KF5503-15 trial (in subjects with moderate to severe chronic malignant tumor-related pain) using a conditional power prior approach (see e.g., Neelon and O'Malley, 2010) with a down-weighting factor $a = 0.4$ (see below for details on the prior elicitation for the treatment effect). The prior for the subject-specific random effects ε_i will be normal $(0, \sigma^2)$. A half-t distribution ($\text{delta}=0$, $\text{var}=10$, $\text{df}=3$) will be used as prior for the precision of the random effects σ . The half-t distribution is defined as the absolute value of a Student-t distribution centered at zero and is recommended as a prior distribution for the hierarchical standard deviation when the number of groups is small (see Gelman 2016 and Chen et al. 2016).

The posterior distribution for the regression coefficients will not have an analytically closed form. Therefore, Markov chain Monte-Carlo (MCMC) methods will be used to obtain a sample from the posterior distribution for the difference between the response rates in tapentadol PR and morphine PR groups. One MCMC chain of length 1,100,000 will be run, discarding the first 100,000 and keeping every 50th. The resulting thinned sample of size 20,000 will be summarized for each model parameter by means of the posterior mean, median, standard deviation and 80% credibility interval. The difference $p_T - p_C$, where p_T and p_C are the response rates in the Tapentadol

and Morphine arms, respectively, will also be computed at each MCMC iteration to obtain a sample from its posterior distribution. To this end, at each MCMC iteration, a value for both response rates (on the log-odds scale) will be calculated as follows:

1. Compute:

$$\eta_T = \beta_0 + \beta_1 \overline{\text{ageg}} + \beta_2 \overline{\text{cancer}} + \beta_3 (\overline{\text{ageg}} * \overline{\text{baseline VAS}}) + \beta_4 (1 - \overline{\text{ageg}}) * \overline{\text{baseline FPS-R}}$$

$$\eta_C = \beta_0 + \beta_1 \overline{\text{ageg}} + \beta_2 \overline{\text{cancer}} + \beta_3 (\overline{\text{ageg}} * \overline{\text{baseline VAS}}) + \beta_4 (1 - \overline{\text{ageg}}) * \overline{\text{baseline FPS-R}} + \beta_5$$

where $\overline{\text{ageg}}$ is the proportion of subjects aged 12 years to less than 18 years, $\overline{\text{cancer}}$ is the proportion of subjects with cancer pain, $\overline{\text{baseline VAS}}$ is the average baseline VAS pain for subjects aged 12 years to less than 18 years, and $\overline{\text{baseline FPS-R}}$ is the average baseline FPS-R pain (for subjects aged 6 years to less than 12 years).

2. Compute $p_T = \exp(\eta_T) / (1 + \exp(\eta_T))$ and $p_C = \exp(\eta_C) / (1 + \exp(\eta_C))$.

Then compute the difference $p_T - p_C$. At the end of the MCMC run, the posterior sample of size 20,000 for $p_T - p_C$ will be also summarized together with the model parameters. If the lower limit of the 80% credibility interval for the difference of the 2 response rates $p_T - p_C$ is >-0.2 , then this would support non-inferiority by this sensitivity analysis.

Elicitation of the prior distribution for the treatment effect

The KF5503-15 trial carried out in adult population included a secondary endpoint to compare the proportion of responders in the Tapentadol and Morphine treatment arms after the 2-week titration period. The response definition in that trial was comparable to the response definition considered in the present trial. It included criteria on trial completion and pain reduction. It also included a condition on the maximum limit for the rescue medication intake, which is not the case in the present study. When recalculating the response rates in the PPS of the KF5503-15 trial without the condition limiting the amount of rescue medication intake, we obtained that 83% of the 100 subjects in the Morphine arm and 81% of the 229 subjects in the Tapentadol arm responded to treatment.

As before, let p_T and p_C be the response rates in the Tapentadol and Morphine arms, respectively. Assuming for both a non-informative prior Beta(0.5, 0.5) and based on the above results of KF5503-15, the posterior distribution obtained using the conditional power approach for a certain down-weighting factor α are:

$$p_T \sim \text{Beta}(\alpha * 100 * 0.83 + 1, \alpha * 100 * (1 - 0.83) + 1)$$

$$p_C \sim \text{Beta}(\alpha * 229 * 0.81 + 1, \alpha * 229 * (1 - 0.81) + 1)$$

Considerations on similarities and differences in the design characteristics of the KF5503-15 trial and the present study led to assume a value for the down-weighting factor of $\alpha=0.4$, which in a way can be interpreted as borrowing 40% of the information from the adults trial to set the prior distribution for the treatment effect in the pediatric population.

The log-odds ratio $b = \log\left(\frac{p_C}{1-p_C}\right) - \log\left(\frac{p_T}{1-p_T}\right)$, should be informative of the treatment effect β_5 , because it can be seen as an unadjusted log-odds ratio. Therefore, to obtain the prior for β_5 , we generated 10,000 values from the posterior distributions of p_C and p_T and used them to obtain a sample from the posterior distribution of the quantity b above. The resulting mean of 0.10 and standard deviation of 0.48 were used to set the prior for β_5 .

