- As time to discontinuation refers to discontinuation from *treatment*, it was specified that the dates of first and last IMP intakes should be used for the respective calculations rather than the dates of the scheduled visits.
- The protocol specifies that subjects should have taken their last IMP of the Treatment Period on the day of VE or the evening before. In reality; this intake might have occurred earlier, in particular for subjects that discontinued treatment. For the derivation of the primary endpoint, it was therefore specified that the last 3 days of treatment should be considered for pain assessment rather than the last 3 days prior to VE.
- The options of the multiple imputation were specified more clearly, covering how the imputation by treatment group should be done, which variables to be included in the model and how to handle the different pain scales and the ranges of their respective scores.
- The prior distribution for the precision of the random effects used in the Bayesian analysis of the primary endpoint was redefined based on the expert recommendation provided in the literature (Gelman 2016).
- The factor for the morphine PR equivalent of tapentadol PR that has to be used for some calculations was added.
- A specification of days to be considered for the SOWS (Day 0 = day of last IMP) was added, as deviating from trial day definition.
- For the Z-score related to *weight* and *height*, a rule to derive the age in months based on the available information in years was provided as required for the calculation.

7.2.2 Amendment 01

Amendment 01 to the final SAP was prepared to cover the following topics:

- Changes arising from protocol Amendment 02 dated 23 June 2015 and protocol Amendment 04 dated 23 May 2017 were implemented, including the following major changes:
 - The update of the alpha for the primary endpoint analysis based on the methodology proposed by Hlavin et al. (2016) with the consequence of sample size reduction and use of 80% confidence interval for the primary endpoint analysis.
 - The deletion of the interim analysis for the sample size reassessment due to the sample size reduction. The adaptive 2-stage design of the trial has been simplified to a fixed 1-stage design.

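### The subject-level random effect in the Bayesian sensitivity model lets the treatment prior override the data, so the rule reports support even at a true deficit twice the margin

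*SAP*

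**What the plan says.** SAP 13.1.2, item 5, lists a Bayesian logistic regression among the sensitivity analyses of the primary endpoint, using the responder status from item 3. SAP 18.1.8.3 specifies it:

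- Each subject has one Bernoulli response. The logit contains an intercept, age group, cancer pain, baseline VAS (older group), baseline FPS-R (younger group), treatment (morphine coded 1) and a term ε_i for each subject.
- "Non-informative flat normal priors with zero mean and variance equal to 1000 will be assigned to the regression coefficients" β_1 to β_4. No prior is stated for β_0.
- β_5 has "a normal distribution with mean = 0.10 and standard deviation = 0.48", derived from an adult cancer-pain trial down-weighted by 0.4. The underlying log odds ratio is taken as informative for β_5 "because it can be seen as an unadjusted log-odds ratio".
- "The prior for the subject-specific random effects" ε_i is normal with variance σ². The half-t prior for σ (var 10, df 3) is justified by a recommendation for use "when the number of groups is small".
- At each MCMC iteration "a value for both response rates (on the log-odds scale) will be calculated as follows": linear predictors at mean covariates, with ε_i left out. If the lower 80% credibility limit of p_T − p_C exceeds −0.2, "then this would support non-inferiority by this sensitivity analysis".

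Protocol 14.2.6.1 has the same random effect with a Gamma prior on its precision. SAP 7.2.1 discloses that change: "The prior distribution for the precision of the random effects used in the Bayesian analysis of the primary endpoint was redefined". The effect itself was kept.

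**The concern.** A subject-level effect needs repeated observations per subject. Here there are up to 69 groups of one, so σ is not identified without covariates and is informed only through the shape of the link with them. A recommendation for few groups does not describe this case.

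Adding ε_i also changes what β_5 means. It becomes a log odds ratio conditional on the subject's own effect, while its prior describes an unadjusted one. The larger σ becomes, the tighter that prior is on the scale where it was elicited. If σ grows without check, the reported support comes from the prior rather than from the trial, and an analysis meant to test the robustness of the primary result would agree almost whatever the data show.

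**Working it through.** **1. The plan's own prior reproduces.** Drawing from Beta(0.4·n·p + 1, 0.4·n·(1 − p) + 1) with 83% of 100 (morphine) and 81% of 229 (tapentadol), logit(morphine) − logit(tapentadol) has mean 0.101 and SD 0.486, against the stated 0.10 and 0.48. No random effect enters this derivation. (In the printed Beta lines the two arms carry each other's data, but the sign of the prior mean is right for morphine coded 1.)

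**2. Scale of β_5.** With a normal random effect the data inform approximately β/k, where k = √(1 + 0.346σ²).

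- At the half-t prior median (squared scale 10), σ = 2.42: k = 1.74, and the prior SD on the unadjusted scale is 0.48/1.74 = 0.276.
- At σ = 50: k = √866 = 29.4, and the prior SD is 0.48/29.4 = 0.016.

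**3. Why σ rises.** Raising σ and scaling β_0 to β_4 by k leaves the fit almost unchanged. Each vague coefficient then contributes a volume factor of about k, so k⁵ if β_0 is also vague. The half-t tail with 3 df falls only as σ⁻⁴. The product grows with σ until the coefficients reach their prior SD, √1000 = 31.6.

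**4. What the rule then does.** For β_5 > 0, expit(η) − expit(η + β_5) is never below −tanh(β_5/4), whatever η is. Crossing −0.2 therefore needs β_5 > 4·atanh(0.2) = 0.811. The 90th percentile of the prior is 0.10 + 1.2816 × 0.48 = 0.715, which gives a bound of −0.177, so the prior alone satisfies the rule. In one run at true 40% vs 80%, using average posterior moments and a normal approximation:

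- without ε_i, β_5 had mean 0.838 and SD 0.370: 90th percentile 0.838 + 1.2816 × 0.370 = 1.312, bound −0.317;
- with ε_i, mean 0.153 and SD 0.482: 90th percentile 0.771, bound −0.190. This is close to the prior despite a 40-point deficit.

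**5. Simulation.** From the documents: 46/23 subjects and the model, priors and rule above. Assumed, because the documents do not give them: one third aged 6 to <12; 25% cancer pain; baseline VAS mean 50, SD 25; FPS-R mean 5, SD 2.5; no covariate effect on response; β_0 ~ N(0, 1000). The half-t was read three ways: squared scale 10, variance 10, or placed on the precision. Each setting used 100 or 200 data sets.

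| True tapentadol vs morphine | Support without ε_i | Support with ε_i |
|---|---|---|
| 60% vs 80% | 61% | 100% (all three readings) |
| 50% vs 80% | 23% | 100% (variance reading) |
| 40% vs 80% | 1% | 98–100% |

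The posterior median of σ at 60% vs 80% was 58, 57 and 143 for the three readings, against prior medians of 2.4, 1.4 and 0.64.

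For an observed 25/46 vs 18/23 (−23.9 points) over 100 covariate draws, the mean lower limit was −0.214 without ε_i (15% support) and −0.003 or −0.005 with it (100%). For 18/46 vs 18/23 (−39.1 points) it was −0.302 (0%) and −0.048 or −0.056 (100% and 98%).

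**6. Robustness of the contrast.**

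- Repeat runs with separately written code and other covariate mixes gave 58–66% without and 100% with at 60% vs 80%; at 40% vs 80%, 0–5% without and 96.5–100% with.
- At 60% vs 80% under the variance reading, support with ε_i stayed at 100% with moderate or strong baseline effects, other age and cancer mixes, and a β_0 prior SD of 2.5. Without ε_i it was 52–62% across the covariate settings.
- The least extreme variant at 40% vs 80% (β_0 prior SD 2.5) still gave 83%. Averaging over ε_i instead of setting it to zero gave 91% there, so the zero-effect rates are not the cause.
- A sampler keeping every ε_i gave a lower limit of −0.011, against −0.012 with ε_i integrated out and −0.220 with no random effect, on the same data set.

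**The case against.** The random effect does not do this alone. In a model with only intercept and treatment, adding it raises support at 60% vs 80% from 58% to 65–84%, and support at 40% vs 80% is only 5–13.5%. The failure needs the vague coefficient priors as well. That is correct, but the SAP specifies both.

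It follows that deletion is not the only remedy. Keeping ε_i and tightening the β_0 to β_4 priors (illustrative SDs 2.5, 2.5, 2.5, 0.1 and 1.0) cut support at 40% vs 80% to 17–34%. At 60% vs 80% it stayed at 93–97%, so deletion is cleaner.

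The output would also give a warning. The SAP asks for posterior summaries of each model parameter, so if σ and β_5 are monitored, a reader could see σ near 50–60 and β_5 almost at its prior. It is the yes/no support statement that is uninformative, not every line of output.

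Finally, this is one of six sensitivity analyses. Item 3 analyses the same responder status without borrowing or a random effect. Calling σ a precision is a minor slip, since the next sentence refers to a standard deviation.

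**Conclusion.** The concern holds: the model is wrong as written. With the planned covariates and priors, the support rule is met in 96.5–100% of simulated trials at a true deficit of 40 points (83% in the least extreme variant). The same model and treatment prior without the random effect gives 0–5%. At the 20-point margin the contrast is 100% against about 60%.

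The exact percentages rest on assumed covariate distributions and an assumed β_0 prior. The contrast held across every variation tried, and the mechanism follows from the printed model. The disclosed factor of 0.4 does not cover it, because the fitted model lets the prior largely replace the data rather than borrow 40% of the adult information. The primary Farrington-Manning decision, its type I error and the sample size are unaffected, so this should be corrected but does not threaten the main conclusion.

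**What to change.** In SAP 18.1.8.3, delete ε_i and its half-t prior. Keep the down-weighted prior on β_5 and the remaining terms, and state the prior for β_0. Record the deletion in SAP 7.1, now marked as not applicable, as a departure from protocol 14.2.6.1, or amend the protocol. A run without borrowing and the prior-only interval would be optional additions.

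The cost is wording and one documented departure, with no extra analyses. The Bayesian result will look less favourable. It will still not be a calibrated test of the margin: support of about 60% at true 60% vs 80% remains because of the disclosed borrowing, and the report should say so.
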